**CONFIDENTIAL**

205665

A listing of which participants reported specific adverse events will be produced.

The hierarchical relationship between MedDRA SOCs, PTs and verbatim text will be listed for all adverse events.

Adverse events occurring during the 24-hour acute challenge will be grouped in the appropriate acute challenge phase. Any AE occurring after AC2 but before repeat-AC2 will be grouped in the HGB maintenance phase.

Adverse events occurring after the last on treatment date will be grouped either in early withdrawal or follow-up depending on the final status of the subject,

*Serious and Other Significant Adverse Events*

The number and percentage of participants and the number of occurrences of SAEs will be provided for each treatment group. These events will be summarized by treatment group, primary system organ class, and preferred term. Pre-treatment, post-randomization, treatment emergent and follow-up SAEs will be summarized separately. Treatment emergent SAE preferred terms will also be summarized by treatment group and overall frequency.

A listing of reasons for considering as a SAE will be produced for all treatment emergent SAEs.

The number and percentage of participants and the number of occurrences of treatment emergent drug-related SAEs, and drug-related fatal SAEs will be summarized by treatment group.

A listing of treatment emergent fatal SAE records and a listing of treatment emergent non-fatal SAE records will be provided.

The number and percentage of participants reporting treatment emergent AEs leading to discontinuation of randomized treatment will be summarized by treatment group, primary system organ class, and preferred term.

A listing of treatment emergent AEs leading to discontinuation of randomized treatment will be provided.

## **8.2. Adverse Events of Special Interest Analyses**

A comprehensive list of MedDRA terms based on clinical review will be used to identify each type of event. [Changes to the MedDRA dictionary may occur between the start of the study and the time of reporting and/or emerging data from on-going studies may highlight additional adverse events of special interest, therefore the list of terms to be used for each event of interest and the specific events of interest will be based on the safety review team (SRT) agreements in place at the time of reporting.] The details of the planned displays are provided in [Appendix 12: List of Data Displays](#). See Section [14.6.4](#) for complete list of AESIs

Summaries of AESIs will include the number, percentage and rate per 100 person-years of participants having at least one occurrence, the number of events, the number of participants by number of occurrence, the characteristics of the AE (serious, drug-related, etc.), outcome, maximum intensity, time to first onset/worsening, the duration of first, second, and third occurrence of the AE, and action taken summarized by treatment group. For each count, a participant will be summarized as follows:

- Serious/drug-related/severe/fatal: If any specific AE falls in the respective category, the participant will be counted in that category.
- Outcome: The participant will be counted within a category if there is at least one specific AE in that category.
- Maximum intensity: The specific AE with the maximum intensity will be counted for this purpose. For example, a participant will be counted in the ‘severe’ category if there is at least one specific AE with severe intensity. A participant will be counted in the ‘moderate’ category if there is at least one specific AE with moderate intensity and there is no specific AE with severe intensity.
- Time to first onset/worsening (days): The earliest of onset dates for the specific AE – treatment start + 1
- Duration of the occurrence (days): AE resolution date – AE onset date/AE worsening date + 1 for the occurrence

If the AE onset date/AE worsening and/or resolution date is missing or incomplete in the database for any occurrence of the specific AE, time to first onset/worsening and/or duration of the first, second, and third occurrence will be left missing for the participant. These summaries of special interest AEs will be provided for those AEs classified as treatment emergent, follow-up and post-randomization.

Kaplan-Meier plots may be produced for each special interest AE summarizing the time to first occurrence of the special interest AE by treatment group.

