4. STUDY DESIGN

4.1. Overall Design

This study will be an open-label, randomized, parallel-group design in HD subjects with anemia associated with CKD. There will be a screening period, a 2-week ESA washout

period, an initial 24-hr Acute Challenge, an 8-week Hgb-maintenance period, a second 24-hr Acute Challenge and a follow-up visit 14±3 days after completing treatment. The study design is outlined in [Figure 1](#).

Figure 1 Study Design

Subjects will be screened for eligibility within 7-30 days prior to the start of an ESA washout period.

Subjects that qualify for enrolment will be washed out of their ESA for 2 weeks; the start of the ESA washout should be timed to coincide as closely as possible with their next planned ESA dose. Subjects are enrolled once they enter the ESA washout period.

Following the 2-week ESA washout, subjects will be randomized 1:1 and stratified by prior ESA dose, based on the average weekly (for epoetins or darbepoetin) or monthly (for methoxy polyethylene glycol (PEG)-epoetin beta) dosing during the 12 weeks prior to ESA washout as follows:

- Low ESA dose: <100 U/kg/week epoetin alfa OR <0.5 µg/kg/week darbepoetin OR <0.6 µg/kg/week methoxy PEG-epoetin beta
- High ESA dose: ≥100 U/kg/week epoetin alfa OR ≥0.5 µg/kg/week darbepoetin OR ≥0.6 µg/kg/week methoxy PEG-epoetin beta

On Day 1, subjects will be randomized and undergo Acute Challenge 1, a single dose challenge to compare the acute effects on BP of the highest planned once-daily maintenance dose of daprodustat (24 mg) to the highest starting dose of epoetin alfa (100 U/kg). Subjects will have BP monitored for 24 hr using ABPM, and will have serial blood sampling to assess the pharmacokinetics of daprodustat and the time-course of various biomarkers. Acute Challenge 1 will be started promptly following completion of a mid-week dialysis session.

After completing Acute Challenge 1, all subjects will enter the 8-week Hgb maintenance period where doses of either daprodustat or epoetin alfa will be administered and adjusted, as needed, based on dosing guidance as described in [Section 6.4](#).

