7.3.1.1. Time Period and Frequency for Collecting AE and SAE Information

- Any SAEs assessed as related to study participation (e.g., protocol-mandated procedures, invasive tests, or change in existing therapy) or related to a GSK product will be recorded from the time a subject consents to participate in the study up to and including any follow-up contact.
- AEs will be collected from the start of washout until the follow-up contact (see Section 7.3.1.3), at the timepoints specified in the Time and Events Table (Section 7.1).
- Medical occurrences that begin prior to the start of washout but after obtaining informed consent may be recorded on the Medical History/Current Medical Conditions section of the CRF.
- All SAEs will be recorded and reported to GSK within 24 hours, as indicated in Section 12.4. The investigator will submit any updated SAE data to the sponsor within 24 hours of it being available.
- Investigators are not obligated to actively seek AEs or SAEs in former study subjects. However, if the investigator learns of any SAE, including a death, at any time after a subject has been discharged from the study, and he/she considers the event reasonably related to the study treatment or study participation, the investigator must promptly notify GSK.

NOTE: The method of recording, evaluating and assessing causality of AEs and SAEs plus procedures for completing and transmitting SAE reports to GSK are provided in Section 12.4.

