**14.4.2. Treatment Emergent Flag for Adverse Events**

All AEs (non-serious AEs and serious AEs) will be collected and recorded on the eCRF from the start of treatment, including washout period, until the follow-up visit at the time points specified in the SoA from [Appendix 2](#). Serious AEs assessed as related to study participation (e.g., study treatment, protocol-mandated procedures, invasive tests, or change in existing therapy) or related to a GSK product will be recorded on the eCRF from the time a participant consents to participate in the study up to and including any follow-up contact.

Treatment State	Definition
Pre-treatment	
 
For participants with a non-missing screen failure date, if AE onset is on or before the screen failure date: AE Start Date <math>\leq</math> Screen Failure Date
 
For randomized participants with a missing treatment start date, all AEs are considered pre-treatment
 
For randomized subjects with a non-missing treatment start date, if AE onset date is before treatment start date: AE Start Date <math><</math> Treatment Start Date
 

Post-randomization	If AE onset date or AE worsening date is on or after the randomization date Randomization date $\leq$ AE Start Date Randomization date $\leq$ AE Worsening Date
Treatment emergent	If AE onset date or AE worsening date is on or after treatment start date & on or before the last non-zero dose date plus 1 day. Treatment Start Date $\leq$ AE Start Date $\leq$ Last Non-Zero Dose Date + 1 day Treatment Start Date $\leq$ AE Worsening Date $\leq$ Last Non-Zero Dose Date + 1 day
Follow-up	If AE onset date or AE worsening date is after the last non-zero dose date plus 1 day. AE Start Date $>$ Last Non-Zero Dose Date + 1 day AE Worsening Date $>$ Last Non-Zero Dose Date + 1 day
Onset /Worsening Time Since 1 st Dose (Days)	If Treatment Start Date $>$ AE Onset Date = AE Onset Date - Treatment Start Date + 1 If Treatment Start Date $\leq$ AE Onset Date = AE Onset Date - Treatment Start Date + 1 If Treatment Start Date $>$ AE Worsening Date = AE Worsening Date - Treatment Start Date If Treatment Start Date $\leq$ AE Worsening Date = AE Worsening Date - Treatment Start Date + 1 Missing otherwise.

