#### 14.6.4. Safety

Adverse Events
AEs of Special Interest

Adverse events of special interest are classified as follows:
 
 
• Death, MI, stroke, heart failure, PE, DVT, thromboembolic events, thrombosis of vascular access
 
• Thrombosis and/or tissue ischemia secondary to excessive erythropoiesis
 
• Cardiomyopathy
 
• Pulmonary artery hypertension
 
• Cancer-related mortality and tumor progression and recurrence
 
• Esophageal and gastric erosions
 
• Proliferative retinopathy, macular edema, choroidal neovascularization
 
• Exacerbation of rheumatoid arthritis
 
• Worsening of hypertension
 
 
The above list text can be shortened for displays as follows:
 
 
• Fatal, CV, and thromboembolic events
 
• Excessive erythropoiesis sequelae
 
• Cardiomyopathy
 
• Pulmonary artery hypertension
 
• Cancer progression or recurrence
 
• Esophageal and gastric erosions
 
• Retinal and choroidal neovascularization
 
• Exacerbation of rheumatoid arthritis
 
• Worsening of hypertension
 

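### SAP 8.2 times adverse events of special interest from onset only and blanks a whole participant's durations for one missing date, giving zero or negative times, short-biased durations and conflict with other SAP sections

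*SAP*

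**What the plan says.** SAP 8.2 defines time to first onset/worsening as "The earliest of onset dates for the specific AE", less treatment start, plus 1. The label covers worsening; the formula does not. Duration is the resolution date minus the onset or worsening date, plus 1, without saying which start date applies when a record has both.

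On missing data, SAP 8.2 says that if an onset/worsening or resolution date is absent or incomplete for any occurrence, "time to first onset/worsening and/or duration of the first, second, and third occurrence will be left missing for the participant".

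On scope, SAP 8.2 states: "These summaries of special interest AEs will be provided for those AEs classified as treatment emergent, follow-up and post-randomization". SAP 14.4.2 sets the treatment-emergent class: "If AE onset date or AE worsening date is on or after treatment start date", up to one day after the last non-zero dose. It also has a row for time since first dose, with separate branches for onset and worsening dates.

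Two other sections deal with missing dates. SAP 14.6.4 (General Definitions) counts a missing onset/worsening date as 1 day. SAP 14.7.2.1 imputes partial dates for time to onset and duration, and leaves completely missing dates missing.

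The AESI list in SAP 14.6.4 includes "Worsening of hypertension".

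**The concern.** An event can enter the AESI summary because it worsened on treatment, yet be timed from an onset before treatment. The result is not a time on treatment, and a time-to-event method cannot place an event before time zero.

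The blanking rule has a different effect. An ongoing event has no resolution date, so one open occurrence removes that participant's durations, including those of earlier occurrences with complete dates. Long events are less likely to have a resolution date, so the remaining durations lean short.

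The competing missing-date rules would also let two programmers following the SAP produce different values from the same record.

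**Working it through.** The plan gives no figure for these rules, so there is none to reproduce. The check is date arithmetic, then an illustration of the duration bias.

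**Can a pre-treatment onset be in the data?** Yes. Protocol 7.3.1.1: "AEs will be collected from the start of washout until the follow-up contact". Washout lengths:
- 14 days. Protocol 4.1: "Subjects that qualify for enrolment will be washed out of their ESA for 2 weeks".
- 21 days (14 + 7), if high hemoglobin on Day 1 extends washout by a week (Protocol 7.5.1.1).
- 28 days, for participants before Amendment 3, whose washout ran from Week -4 to Day 1 (SAP 5.1). This case assumes that their adverse events were collected through washout.

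**Time to first.** With onset d days before treatment start, SAP 8.2 gives −d + 1 = 1 − d. The worsening-date branch in SAP 14.4.2 gives worsening date − treatment start + 1. For worsening on Day 20:

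| Onset | SAP 8.2 | Worsening-date branch |
|---|---|---|
| 1 day before treatment | −1 + 1 = 0 | 20 |
| 10 days before | −10 + 1 = −9 | 20 |
| First day of 14-day washout | −14 + 1 = −13 | 20 |
| First day of 21-day washout | −21 + 1 = −20 | 20 |
| First day of 28-day washout | −28 + 1 = −27 | 20 |

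**Duration start date.** Take onset 10 days before treatment, worsening on Day 20 and resolution on Day 30. Duration is 40 days from onset (10 days before treatment plus Days 1 to 30) and 11 days from worsening (30 − 20 + 1). SAP 8.2 permits either.

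**Duration bias.** A simulation under assumptions that are not in the documents: one occurrence per participant, onset uniform over Days 1 to 57, exponential durations, and follow-up closing on Day 71 (57 + 14).

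| True mean (days) | Share open at Day 71 | Observed mean, all open events dropped | Observed mean, 80% of open events later followed to resolution |
|---|---|---|---|
| 7 | 2% | 6.6 | 6.9 |
| 14 | 9% | 11.3 | 13.5 |
| 30 | 28% | 16.6 | 28.0 |
| 60 | 51% | 20.0 | 55.6 |

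The direction is short in every row. The size runs from negligible to large, depending on true duration and completeness of follow-up. With one occurrence each, the simulation does not include the further loss of fully dated occurrences.

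**Missing-date rules side by side.**
- Onset/worsening date completely missing: time to onset is missing under 8.2 and 14.7.2.1, but 1 day under 14.6.4.
- Date partial: values are missing under 8.2, but imputed under 14.7.2.1.
- Resolution date missing: 8.2 acts on the participant, whereas 14.7.2.1 leaves only that event's duration missing. The and/or in 8.2 does not settle whether time to first is blanked too.

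**The case against.** The best reply is that the SAP already holds the right calculation. SAP 14.4.2 has a worsening-date branch that gives 20 in the example, and the label in 8.2 suggests the same intent. That makes this a matter of reconciling sections, but it does not remove the problem. The next item in 8.2, on duration, names both dates, so onset alone cannot safely be read as shorthand. Section 14.4.2 also has an onset branch and does not say which branch governs when a record has both dates.

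The reply is stronger on consequences, where three wider readings are tempting.

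- *That timing for worsening of hypertension would generally be wrong.* The documents do not support this. Participants enter on at least one antihypertensive (Protocol 5.2). Exacerbation of a pre-existing condition is an adverse event in its own right (Protocol 12.4.1), and conditions arising before washout may go in medical history (Protocol 7.3.1.1). On-treatment worsening of established hypertension would normally be a new record with an on-treatment onset, which 8.2 times correctly. The error needs an AESI that begins during washout and worsens under the same record.
- *That late events will often still be open.* Protocol 7.3.1.3 follows AESIs beyond the 14-day visit, to resolution, stabilization, another explanation or loss to follow-up. That reduces the bias. It does not remove it, because an AESI closed for any reason other than resolution may still have no resolution date.
- *That key outputs would fail.* Kaplan-Meier plots are optional. Appendix 12 lists one AESI table (2.11, shell AE1) and no safety figures. Unresolved events also remain visible through the outcome summary and the adverse event listings.

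**Conclusion.** The concern holds as a defect in stated rules. Read literally, SAP 8.2 gives zero or negative times for AESIs that begin in washout and worsen on treatment, with minimum −13, −20 or −27 days by washout length. Its participant-level blanking discards usable durations and biases the rest short, because the chance of having a resolution date falls as duration rises. The size of that bias is unknown; the simulated figures show a range under assumed distributions and are not estimates for this trial. Exclusion because an onset date is missing has no fixed direction of bias. The conflict with 14.6.4 and 14.7.2.1 stands on the text alone.

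The reach is small: descriptive AESI summaries and optional plots. No test or decision uses these values, the primary analysis is unaffected, and the documents do not show how many events would be involved. It is worth correcting because the rules yield wrong values and the correction is cheap.

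**What to change.** 1. In SAP 8.2, define time to first onset/worsening as the earliest onset or worsening date on or after treatment start, minus treatment start, plus 1. Point to the worsening-date branch in 14.4.2, and state there which branch applies when both dates exist.
2. Derive duration separately for each occurrence, name the start date used, and leave the participant's other occurrences intact when one lacks a date.
3. Report unresolved occurrences as ongoing. Where a time-to-event method is used for duration, censor them at the last study contact date, already defined in 14.6.1.
4. Choose one rule for missing and partial dates and apply it in 8.2, 14.6.4 and 14.7.2.1.

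The cost is a few sentences of SAP text and matching derivation code. No new data are needed.

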### **8.3. Clinical Laboratory Analyses**

Laboratory evaluations including the analyses of Chemistry laboratory tests, Hematology laboratory tests, Urinalysis, and liver function tests will be based on GSK Core Data Standards. The details of the planned displays are in [Appendix 12: List of Data Displays](#) and include the following tests:

**CONFIDENTIAL**

205665

Laboratory Assessments	Parameters		
Hematology	Platelet Count	RBC Indices:	WBC Count with Differential:
	RBC Count	MCV	Neutrophils
	Hemoglobin	MCH	Lymphocytes
	Hematocrit	MCHC	Monocytes
	WBC Count (absolute)	RDW	Eosinophils
	Reticulocyte Count	CHr	Basophils
Clinical Chemistry	Potassium	AST (SGOT)	Total and direct/indirect bilirubin
	Sodium	ALT (SGPT)	Total Protein
	Glucose	Calcium (Albumin adjusted)	Alkaline Phosphatase
	Albumin	Phosphate	
Other Screening Tests	Serum hCG pregnancy test	Serum ferritin	Folate
	Estradiol	Serum iron	Vitamin B12
	FSH	Serum transferrin	UIBC
		TSAT	

The clinical chemistry tests performed in this study include ALT, AST and bilirubin. In addition to being summarized with the clinical chemistry values, these laboratory values will be included in some of the Hepatobiliary (liver) displays.

In addition to the visits listed for the laboratory assessments in the Schedule of Activities (see Section 14.2.1), any of these assessments can be performed at an unscheduled/retest visit or at the follow-up visit at the discretion of the investigator. See Section 14.5.2 for handling of unscheduled values. The laboratory's normal range values will be provided by the central laboratory and potential clinical importance thresholds are defined in Section 14.8.1.

In addition to the other screening tests, serum iron will also be collected and summarized similar to the parameters listed in the table above. Both ferritin and serum iron will be log transformed.

HGB will be summarized with both the central lab and local lab (Hemocue).

All of the tabular summaries described below will include summaries in SI units and conventional units for the following laboratory tests: hemoglobin, MCHC, albumin-adjusted calcium, phosphate, and albumin. Conversions from SI units to conventional units are included in Section 14.6.4.

The clinical laboratory safety analyses will be based on the Safety population and GSK Core Data Standards, unless otherwise specified. The details of the planned displays are in [Appendix 12: List of Data Displays](#).

#### **8.4. Other Safety Analyses**

The analyses of non-laboratory safety test results including ECGs and vital signs will be based on GSK Core Data Standards, unless otherwise specified. The details of the planned displays are presented in [Appendix 12: List of Data Displays](#).

The analyses of non-laboratory safety test results including vital signs, concomitant medications and meeting protocol defined stopping criteria (e.g., liver chemistry) will be based on GSK Core Data Standards, unless otherwise specified. The details of the planned displays are presented in [Appendix 12: List of Data Displays](#).

Vital signs and weight are assessed in this study according to the schedule outlined in the Time and Events table (see Section [14.2.1](#)) and include the following assessments:

- Temperature
  - SBP
  - DBP
  - HR
  - MAP
  - Weight (pre- and post-dialysis)

The vital signs analyses will be based on the Safety population, unless otherwise specified.

Vital signs will be summarized for both pre and post dialysis recordings.

Vital sign values will be summarized using mean, standard deviation, minimum, P25, median, P75, and maximum for each scheduled visit and for baseline and end of treatment by treatment group.

Vital sign change from baseline values will be summarized using mean, standard deviation, minimum, P25, median, P75, and maximum for each scheduled visit.

A listing of all vital signs with PCI criteria for participants with on-treatment vital signs values outside of PCI criteria will be provided for the parameters listed in Section [14.8](#).

Reasons for early study withdrawal and for stopping randomized treatment will also be summarized by treatment group with Table 1.1 and Table 1.2 respectively under study population tables using the enrolled and ITT populations respectively.

Summaries of subjects affected by COVID-19 will be provided. These will include a summary of all treatment emergent adverse events. See [Appendix 12: List of Data Displays](#) for list of summary tables.

